16.6. Study Termination

The Sponsor may terminate the study as a whole or at individual study sites under the following circumstances:

- Suspicion of risk to subjects, including occurrence of high rate of known AEs or unexpectedly high rate of unexpected AEs
- Poor site compliance with the study protocol
- Inadequate site enrollment
- Obtaining new scientific knowledge that shows that the study is no longer valid or necessary
- Persistent non-compliance with IRB or regulatory requirements
- Persistent failure to comply with obligations arising from the clinical trial agreement

Investigational Plan, Protocol CT-05 (Extension Study)

Document #: CT-4

Rev: 1.0

Effective: 11/24/2021

- Insufficient availability of investigational devices
- Other business reasons (e.g., insolvencies or business entity liquidation)

The sponsor will document reasons for study suspension and notify relevant site Investigators and governing IRBs. If suspension occurred because of a safety issue, all Investigators will be notified. When terminating the study, the sponsor and Investigator will assure that adequate consideration is given to the protection of the subjects' interests.

17. Study Endpoints and Analysis Overview

17.1. Treatment of data from the RESTFUL Study

CT-05 is an extension of the RESTFUL Study and Arms 1 and 2 involve a direct roll-over from the RESTFUL Study into CT-05. Therefore, data from the RESTFUL Study (CT-04) will be used to define the Baseline for Arms 1 and 2 and may be used to define subgroup analyses and demographic characterization.

17.2. Efficacy

17.2.1. Primary Efficacy Endpoint

Arm 1: The primary outcome measure will be responder rate on the CGI-I scale at Week 24 of Arm 1 relative to entry to the RESTFUL Study.

Arm 3: The primary outcome measure will be responder rate on the CGI-I scale at Week 24 of Arm 3 relative to CT-05 study entry.

Responder rate for the 7-point CGI-I scale will be defined as the proportion of responses of "Much Improved" or "Very Much Improved".

17.2.2. Key Secondary Efficacy Endpoints

Arm 1:

- 1. PGI-I responder rate (defined as for CGI-I) at Wk-24 relative to entry to the RESTFUL Study.
- 2. Mean reduction in IRLS score at Week 24 of Arm 1 relative to entry to the RESTFUL Study.
- 3. Mean reduction in MOS-II score at Week 24 of Arm 1 relative to entry to the RESTFUL Study.
- 4. Mean reduction in MOS-I score at Week 24 of Arm 1 relative to entry to the RESTFUL Study.
- 5. Frequency of RLS symptoms (based on IRLS question #7) at Week 24 of Arm 1 relative to entry to the RESTFUL Study.

Investigational Plan, Protocol CT-05 (Extension Study)

Document #: CT-4

Rev: 1.0

Effective: 11/24/2021

Arm 3:

1. PGI-I responder rate (defined as for CGI-I) at Week 24 relative to CT-05 study entry.

2. Mean reduction in IRLS score at Week 24 of Arm 1 relative to CT-05 study entry.

3. Mean reduction in MOS-II score at Week 24 of Arm 1 relative to CT-05 study entry.

4. Mean reduction in MOS-I score at Week 24 of Arm 1 relative to CT-05 study entry.

5. Frequency of RLS symptoms (based on IRLS question #7) at Week 24 of Arm 1 relative to CT-05 study entry.

Definition and instructions for calculation of the Medical Outcomes Study Sleep Problems Index I and II are described in [13].

17.2.3. Efficacy Analysis

A Statistical Analysis Plan (SAP) will be developed prior to completion of the first subject in Arm 1 or 3, which will include a plan for efficacy analysis. The following analyses are planned:

- Primary statistical analysis may be conducted separately for subjects in Arms 1 and Arm 3.
 Additional pooled analysis across Arms 1 and 3 may also be conducted.
- Subgroup analysis form Arms 1 and 3 may be conducted based on the following criteria:
 - o Responders at Week-8 of The RESTFUL Study, as defined by CGI-I of 1 or 2.
 - o Non-responders at Week-8 of The RESTFUL Study, as defined by CGI-I of 3 or above.
- Missing data may be addressed with the use of multiple imputation.
- Appropriate statistical techniques will be employed to test statistical significance.
- If there is success on the primary endpoint, then secondary endpoints will be tested in order,
 according to the fixed-sequence method, until failure.

The analysis cohort for the primary efficacy endpoint are subjects who are enrolled and undergo the assigned treatment.

The Per Protocol analysis will exclude subjects for whom one or more of the following apply:

- 1. Dropout or removal from the study.
- 2. Incomplete or missing data for the endpoint.

Clinical Trial

Investigational Plan, Protocol CT-05 (Extension Study)

Document #: CT-4

Rev: 1.0

Effective: 11/24/2021

- 3. Clinically significant change in dose or schedule of medication that affects RLS symptoms.
- 4. New medical information available after randomization indicates an exclusion criterion.
- 5. Other protocol deviation occurs that is deemed clinically significant by the investigator.
- 6. Device usage at or after bedtime on fewer than two-thirds of the nights with RLS symptoms at or after bedtime, as reported by the subject on the Weekly Questionnaire assessments.
- 7. Missing two or more follow-ups (Follow-ups completed out-of-window are not considered "missing")
- 8. Zero total device uses.

17.2.4. Additional efficacy analyses

Comparison of Arm 1 (investigational device) to Arm 2 (control)

Arm 1 and Arm 2 both cover the same period of time – the 24-wks after completion of the RESTFUL Study). Arm 1 involves continual open-label usage of the investigational device throughout this time period, whereas Arm 2 (control) involves no usage of the investigational device. Comparison of the data from these arms will be used to assess how continued use of the devices over 24-weeks impacts RLS symptoms, sleep, and medication use relative to the typical standard of care over 24-weeks.

- For Arm 2, baseline will be defined as entry to CT-04 Restful Study and similar analyses will be conducted as in Arm 1.
- Results from Wk-24 of Arm 2 (no device usage) will be compared to results from Wk-24 of Arm 1 (device usage), to assess the effect of continued device usage on the following outcomes:
 - o Changes in RLS symptoms, as measured by CGI-I, PGI-I, and IRLS
 - Changes in Sleep, as measured by MOS-II and MOS-I
 - Changes in quality of life, as measured by SF-36
 - Changes in the dose and type of concomitant medications prescribed and/or administered to treat RLS

Changes to symptom severity over time

- Linear regression of PGI-I over all weeks of Active treatment*
- Linear regression of IRLS over all weeks of Active treatment*

Investigational Plan, Protocol CT-05 (Extension Study)

Document #: CT-4

Rev: 1.0

Effective: 11/24/2021

- Linear regression of Frequency of RLS symptoms over all weeks of Active treatment* (based on IRLS question #7)
- Linear regression of MOS-II over all weeks of Active treatment*
- Linear regression of MOS-I over all weeks of Active treatment*
- * For Arm 1, this starts at the beginning of Active treatment in the RESTFUL Study. For Arm 3, this starts at entry to Arm 3.

Additional subgroup analyses

- Subjects assigned to Sham control for Weeks 1-4 of the RESTFUL Study
- Subjects assigned to Active treatment for Weeks 1-4 of the RESTFUL Study

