7.1. Screening process differences for each Arm

Investigational Plan, Protocol CT-05 (Extension Study)

Document #: CT-4

Rev: 1.0

Effective: 11/24/2021

All subjects were screened for the eligibility criteria in Sections 7.2 and 7.3 upon entry to The RESTFUL Study, with the exception of IC #13 and EC #25-27. The following subset of eligibility criteria will be re-assessed at screening for CT-05, to confirm that they still apply:

- **Arm 1:** IC #8, 12-13. EC #7, 11*, 12, 14-17, 19, 21-27.
 - * except that acute infections with mild symptoms will not be exclusionary.
- Arm 2: IC #12-13. EC #12, 17, 21, 23, 25.
- **Arm 3:** IC #3-8, 10, 12-13. EC #2, 3, 6-12, 14-17, 19-27.

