7.2. Complete list of inclusion criteria (IC)

All subjects are required to meet the following inclusion criteria in order to be considered eligible for participation in this study:

- 1. Subject has received a medical diagnosis of primary restless legs syndrome (RLS).
- 2. Subject is refractory to RLS medication (as defined in section 7.3).
- 3. Subject has moderate-severe RLS symptoms as defined by a score of 15 or greater points on IRLS (International Restless Legs Syndrome Study Group Rating Scale [12]) over the week prior to study entry.
- 4. Subject has RLS symptoms 2 or more nights per week during the week prior to study entry as defined by a score of 2, 3, or 4 on IRLS question #7.
- 5. RLS symptoms are most significant in the subject's lower legs and/or feet.
- 6. RLS symptoms are most significant at bedtime, after bedtime, and/or in the 2 hours before bedtime.
- 7. RLS symptoms between 10am and 6pm are not severe.
- 8. Subject agrees to not change dosage or schedule of any medications that are known to impact RLS symptoms during the study, including RLS medications, antidepressants, sleep medications, or sedative antihistamines.
- 9. Subject agrees to not make major lifestyle changes during the study that would significantly affect bedtime, such as major changes to diet, exercise, or career.

Investigational Plan, Protocol CT-05 (Extension Study)

Document #: CT-4

Rev: 1.0

Effective: 11/24/2021

- 10. Subject possesses the necessary equipment, internet/phone accessibility, and communication ability to complete electronic questionnaires and respond to electronic communications and phone calls from the research staff throughout the in-home portion of the study.
- 11. Subject is \geq 22 and \leq 79 years of age when written informed consent is obtained.
- 12. Subject has signed a valid, IRB-approved informed consent form, can understand the requirements of the study and instructions for device usage, and can converse in English.
- 13. Subject previously completed the RESTFUL Study.

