16.10. Concomitant Medications and Treatments

Concomitant medications and treatments are tracked throughout the study based on subject reported data. For Arms 1 and 3 (but not Arm 2), study subjects are instructed to maintain a stable dose and schedule of all concomitant medications and treatments for RLS and of all concomitant medications and treatments that affect RLS symptoms, including antidepressants, sleep medications, or sedative antihistamines.

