3.1 Overview

Subjects who previously completed the RESTFUL Study [Protocol Number: CT-04; ClinicalTrials.gov Identifier: NCT04874155] consent to one of two Arms, the design of which is

illustrated in the flowchart below (Figure 1). Arm 1 is a Direct Roll-Over Extension and Arm 2 is a Control.

- **Arm 1** (Direct Roll-Over Extension) Arm 1 is only an option for subjects who successfully complete RESTFUL Study after enrollment to CT-05 begins at a given clinical site; Arm 1 involves a 24-wk extension period of NTX100 device use followed by an 8-wk period without device use. Subjects in Arm 1 are instructed to maintain constant dose and schedule of RLS medication (if applicable).
- Arm 2 (Control Group) Arm 2 is an option for subjects who successfully complete the RESTFUL Study before enrollment to CT-05 begins at a given clinical site or subjects who decline to participate in Arm 1. Subjects enrolled in Arm 2 will receive no treatment with the NTX100 device during Arm 2. Arm 2 involves assessment during the 24-wks after RESTFUL Study completion. Subjects in Arm 2 are permitted to change RLS medication.

Figure 1: Study Design Flowchart

The schedule of assessments for this study is presented in Table 1.

Table 1: Schedule of Assessments

	Eval 1			Eval 2	Eval 3	Eval 4	Eval 5	Eval 6	Eval 7	Eval 8	Eval 9	
	Day 0	Wks 1-24	Wks 25-32	Wk-2	Wk-4	Wk-8	Wk-12	Wk-16	Wk-20	Wk-24	Wk-32	
	In-person	Remote	Remote	Remote	Remote	In-person or Remote**			Remote	In-person	Remote	
Completed by												
	X											
	X											
Staff + subject	X											
Subject		X										
Subject			х									
Staff				X	X	x	X	x	X	X		
Staff	X			Х	Х	x	X	Х	Х	х	X	
Staff				X	Х	x	X	x	X	Х	X	
Staff + subject				Х	Х	x	Х	Х	Х	х	X	
Staff + subject				X	X	x	X	x	X	X	X	
Investigator + subject						х		х		Х	X	
Staff + subject					Х	x	X	Х	х	х	X	
Staff + subject	X									х		
Staff + subject										х		
Staff + subject											X	
Staff + subject	X **					X **		X **				
	* Data from Eval	11 of the RE	STFUL Study	will be us	ed, since b	oth Evals typic	cally occu	r on the same	day			
	Staff + subject Subject Subject Staff Staff Staff Staff Staff + subject Staff + subject Investigator + subject Staff + subject	In-person	Day 0 Wks 1-24 In-person	Day 0	Day 0 Wks 1-24 Wks 25-32 Wk-2	Day 0	Day 0	Day 0	Day 0	Day 0 Wks 1-24 Wks 25-32 Wk-2 Wk-4 Wk-8 Wk-12 Wk-16 Wk-20 In-person or In-pe	Day 0 Wks 1-24 Wks 25-32 Wk-2 Wk-4 Wks-4 Wks-12 Wk-16 Wk-20 Wk-24	Day 0

		Eval 1	Eval 2	Eval 3	Eval 4	

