9.0 OTHER ANALYSES

For each of the following outcome measures (CGI-I responder rate, PGI-I responder rate, IRLS total score, MOS-II score, MOS-I score, IRLS Question #7 score), data will be summarized for:

- Each of Arm 1 and Arm 2 at Week 24 for subjects assigned to each of NTX100 and Sham control in CT-04 Phase 1.
- Each of Arm 1 and Arm 2 at Week 24 compared to CT-05 study entry.
- Each of Arm 1 and Arm 2 at each of CT-04 study entry, CT-04 week 8, CT-05 week 8, CT-05 week 16, CT-05 week 24, [and CT-05 week 32 for Arm 1 only].

For CGI-I and PGI-I, data will be summarized for the proportion of subjects reporting any improvement, as measured by a response of 3 or lower (Minimally improved, Much improved, or Very much improved) and reported for each of Arm 1 Week 24, Arm 1 Week 32, and Arm 2 Week 24.

For MOS Sleep, data will be summarized and effect sizes will be presented for each Arm each of the following dimensions and items for each of CT-04 study entry and CT-05 week 24:

- MOS "Sleep disturbance" dimension (Items 07, 03, 08, 01)
- MOS "Somnolence" dimension (Items 09, 11, 06)
- MOS "Sleep adequacy" dimension (Items 04, 12)
- MOS "Quantity of sleep / Optimal sleep" dimension (Item 02)
- MOS Item 01 (Trouble falling asleep)

For each of the following components of SF-36, data will be summarized and effect sizes will be presented comparing Arm 1 of CT-05 study entry to Arm 1 CT-05 week 24 and comparing Arm 1 CT-05 week 24 to Arm 2 CT-05 week 24:

- Vitality
- Physical functioning
- Bodily pain
- General health perceptions
- Physical role functioning
- Emotional role functioning
- Social role functioning
- Mental health

Consent and completion rates will be presented for Arm 1.

Changes to RLS management: For subjects in each Arm, changes to RLS management will be presented including the following:

- Doctor visits for the management of RLS.
- New prescription medications added for the treatment of RLS.
- Prescription medications discontinued for the treatment of RLS.
- Increases to dosage of prescription medication for the treatment of RLS.

• Decreases to dosage of prescription medication for the treatment of RLS. For each, total numbers of subjects and percentages of subjects will be summarized by Arm from Week 1 to Week 24.

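### Protocol 17.2.4 treats RLS medication change as a measure of device effect, but only Arm 1 is told to hold its medication, so an Arm 1 versus Arm 2 difference cannot be attributed to the device

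*Protocol*

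**What the plan says.** Protocol 17.2.4 (Additional efficacy analyses) sets Week 24 of Arm 2 against Week 24 of Arm 1 "to assess the effect of continued device usage on the following outcomes". The list covers symptoms, sleep, quality of life and, as its last item, "Changes in the dose and type of concomitant medications prescribed and/or administered to treat RLS". The lead-in sentence also names medication use as something on which continued device use is to be judged against standard of care.

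The two arms work under different medication rules:

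- Protocol 16.10: "For Arms 1 and 3 (but not Arm 2), study subjects are instructed to maintain a stable dose and schedule of all concomitant medications".
- Protocol 7.2, IC #8: "Subject agrees to not change dosage or schedule of any medications that are known to impact RLS symptoms during the study". Protocol 7.1 re-assesses IC #8 and EC #19 (which includes planning to change RLS medications) for Arm 1. The list for the control arm reads "Arm 2: IC #12-13. EC #12, 17, 21, 23, 25" and contains neither.
- Protocol 16.16: in Arms 1 and 3 only, a significant dose change in medications that interfere with sleep or RLS symptoms is a possible reason for removal.
- SAP 3.1 and 3.2: Arm 1 is told to keep RLS medication constant (Weeks 1 to 32 in 3.2). For the control arm, "Subjects in Arm 2 are permitted to change RLS medication".

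SAP 9.0 then says: "For subjects in each Arm, changes to RLS management will be presented". The items are doctor visits, drugs added, drugs discontinued, dose increases and dose decreases, as counts and percentages by Arm over Weeks 1 to 24 (Table 2.18, ITT).

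**The concern.** An outcome can show a treatment effect only if the arms are otherwise equally free to have it. Here one arm is told not to have the outcome, confirms that intention at entry, and may be removed if it occurs. The other arm is under no such rule. A device that did nothing would still be expected to sit beside fewer medication changes in Arm 1.

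What is at stake is interpretation. Under the stated purpose of 17.2.4, fewer added drugs or dose increases in Arm 1 could be reported as the device reducing the need for medication. The same instruction also discourages stopping or lowering a drug, so a real medication-sparing effect could be hidden or reversed in the same table.

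**Working it through.** The documents give no sample size, expected rate or power for this outcome, so there is no figure to reproduce. The main check is a comparison of the sections.

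**1. Does the rule coincide with arm?** Yes. Protocol 16.10 and SAP 3.1 and 3.2 assign the stable-medication instruction to Arm 1 and withhold it from Arm 2. Within this comparison, device use and instruction always occur together, so no covariate adjustment could separate them (SAP 5.2 plans none).

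**2. Does the Stable Medication Population repair it?** No. SAP 3.5 and 6.2 add that population because the instructions differ, but apply it to key secondary endpoints #6-11: CGI-I, PGI-I, IRLS, MOS-II, MOS-I and IRLS question 7. It excludes subjects with a new or dose-changed prescription RLS or sleep medication. Applied to medication change, it would remove most of the events being counted.

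**3. How large could the artefact be?** For illustration only, with every input assumed:

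- p = share who would change RLS medication if free to, the same in both arms (no device effect)
- a = share of those in Arm 1 who hold because of the instruction
- Arm 2 rate = p; Arm 1 rate = p(1 − a); expected difference = p × a

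| p | a = 50% | a = 80% | a = 100% |
|---|---|---|---|
| 10% | 5 points | 8 points | 10 points |
| 20% | 10 points | 16 points | 20 points |
| 30% | 15 points | 24 points | 30 points |
| 40% | 20 points | 32 points | 40 points |

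The SAP plans no test of this outcome. To judge whether such gaps would stand out, take an assumed 50 per arm and the SAP's one-sided 0.025 level. The chance of nominal significance is Φ[(d − 1.96·√(2p̄(1 − p̄)/n)) / √((p₁(1 − p₁) + p₂(1 − p₂))/n)]. For p = 20% and a = 80%: p₁ = 0.04, p₂ = 0.20, d = 0.16, p̄ = 0.12. This gives (0.16 − 1.96 × 0.0650)/0.0630 = 0.52, or about 70%, against a nominal 2.5%. With 30 or 80 per arm it is about 48% or 88%.

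**4. Which way does it point?** The formula applies equally to reductions and discontinuations, where a lower Arm 1 rate looks unfavourable to the device. Suppose 20% of Arm 2 reduce or stop a drug, and the device truly raised the share of Arm 1 who would do so to 40%. With a = 80%, Arm 1 shows 40% × 0.20 = 8%. The table would read 8% against 20%, although the true effect was 20 points in the device's favour.

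**The case against.** The strongest reply is that the SAP has already reduced this to description. Medication change is not among key secondary endpoints #1-11. SAP 9.0 attaches no hypothesis, test or device-effect wording to it. The MOS and SF-36 paragraphs of that section call for effect sizes and the RLS-management paragraph does not. Table 2.18 does not carry the Arm 1 vs. Arm 2 label that Table 2.17 does. The differing instructions are stated openly in SAP 3.1, 3.2, 3.5 and 6.2. All of this stands, and it limits the point to interpretation.

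It does not dispose of the point. The device-effect purpose in Protocol 17.2.4 is still in force, and SAP 9.0 gives no caveat. SAP 5.1 also requires effect sizes in every table that compares efficacy outcome measures between Arms 1 and 2. The Protocol lists medication change under additional efficacy analyses, so whether that rule reaches Table 2.18 is unclear.

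A reader might also infer that the instructions fix the outcome in Arm 1 and account for the whole difference. The documents do not support that. Changes in Arm 1 are discouraged, not prevented: concomitant medications are recorded at every Arm 1 evaluation, and the Per Protocol definition provides for Arm 1 subjects who change RLS medication. Removal is discretionary, requires a significant change, and does not name RLS drugs among its examples. A device contribution is not excluded; it cannot be isolated. Nor does either document make a medication-sparing claim.

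Finally, Arm 2 is meant to show medication change under standard of care (Protocol 16.1), and readers need both arms side by side to interpret endpoints #6-11. That argues for keeping the table by Arm.

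**Conclusion.** The point holds as one of attribution. A between-arm difference in RLS medication change, in either direction, cannot be separated from the differing instructions and so cannot answer the question that Protocol 17.2.4 puts to it. This conclusion rests on the documents' own wording and needs no numerical assumption. The size is unknown. The 5 to 40 points in the table depend on assumed p and a and show only that the artefact need not be small; at a = 100% the Arm 1 rate is zero.

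The reach is limited to an additional analysis in the Protocol and an untested summary in the SAP. The primary endpoint, key secondary endpoints #1-11 and the fixed testing sequence are untouched.

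**What to change.** - **Protocol 17.2.4:** remove medication change from the list of outcomes used to assess the effect of device use, and remove *medication use* from the lead-in sentence.
- **SAP 9.0 and Table 2.18:** keep the side-by-side presentation by Arm, with additions, discontinuations, increases and decreases shown separately. Add a footnote such as: *The Arms had different medication instructions: Arm 1 was asked to keep RLS medication constant and Arm 2 could change it. The table is descriptive and no device effect is inferred.*
- **SAP 5.1:** state that the effect-size rule does not apply to Table 2.18.

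No medication rule, data collection or formal test changes. The cost is a few lines of text; the small downside is that the sponsor gives up a device-effect reading of medication change.

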17.3. Safety

17.3.1. Safety Endpoints

The safety endpoint will be a descriptive analysis of adverse events (AEs) for both study arms, classified and tabulated by seriousness, relationship to the device, and severity.

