Study Design	Arm 1 (Direct Roll-Over Extension) — For subjects who successfully complete The RESTFUL Study at or after the initiation of CT-05 at a given clinical site. Arm 1 involves a 24-wk extension period of NTX100 device use followed by an 8-wk period without device use. Arm 2 (Control Group) — For subjects who successfully complete the RESTFUL Study prior to the initiation of CT-05 at a given site or for subjects who choose not to enroll into Arm 1. Subjects enrolled in Arm 2 will not receive treatment with the NTX100 device. Arm 2 involves follow-up phone calls to access RLS progression and medication usage at 8-wks, 16-wks, and 24-wks from the last date of RESTFUL study participation. Arm 3 (Delayed Extension) — For subjects who successfully complete the RESTFUL Study prior to the initiation of CT-05 at a given clinical site. Arm 3 involves a 24-wk extension period of NTX100 device use followed by an 8-wk period without device use. The sponsor will notify each site once Arm 3 is open to enroll study subjects for that site.

[figure not shown]

Investigational Plan, Protocol CT-05 (Extension Study)

Document #: CT-4

Rev: 1.0

Effective: 11/24/2021

Investigational Plan, Protocol CT-05 (Extension Study)

Document #: CT-4

Rev: 1.0

Effective: 11/24/2021

	Responder rate for the 7-point CGI-I scale will be defined as the proportion of responses of "Much Improved" or "Very Much Improved".	
Key Secondary	 PGI-I responder rate (defined as for CGI-I) at Week 24 of Arm 1 relative to entry to The RESTFUL Study. Mean reduction in IRLS score at Week 24 of Arm 1 relative to entry to The RESTFUL Study. Mean reduction in MOS-II score at Week 24 of Arm 1 relative to entry to The 	
Efficacy Endpoints	 RESTFUL Study. Mean reduction in MOS-I score at Week 24 of Arm 1 relative to entry to The RESTFUL Study. Frequency of RLS symptoms (based on IRLS question #7) at Week 24 of Arm 1 relative to entry to The RESTFUL Study. 	
Safety Endpoint	Descriptive analysis of adverse events, classified and tabulated by seriousness, relationship to the device, timing, and severity.	
Adherence outcome measure	Ratio of number of days of device use to number of days with RLS symptoms.	
Summary of subjective assessments	CGI-I, PGI-I, IRLS, MOS-Sleep, SF-36, Weekly questionnaire, Bi-weekly questionnaire, Concomitant medications	

Abbreviations

AE	Adverse Event
AO	Anticipated Observation
CFR	Code of Federal Regulations
CGI-I	Clinical Global Impressions – Improvement
CRF	Case Report Form

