9.1. Investigational device risks

NPNS devices such as NTX100 Neuromodulation System result in a known potential for the following anticipated observations, which are typically mild to moderate, transient in nature, and resolve over time.

- Mild skin irritation from use of adhesive electrodes and/or secondary attachment mechanism.
- Discomfort, paresthesia, or otherwise irritating or uncomfortable sensations during active electrical stimulation.
 - This risk is reduced by calibrating the stimulation intensity.
- Temporary interference with sleep while wearing the device:
 - For some individuals, device may be uncomfortable, thus interfering with sleep while wearing the device.
 - For some individuals, this device may interfere with preferred sleep positions, thus interfering with sleep during usage.
- Temporary increase in RLS symptoms while wearing the device:
 - For some individuals, this device may interfere with voluntary leg movements used to relieve RLS symptoms, thus leading to a temporary increase in RLS symptoms.
 - In some cases, this device may otherwise lead to a temporary increase in RLS symptoms during active stimulation for other reasons.
 - This risk may be reduced by calibrating the stimulation intensity and/or adjusting the schedule of stimulation.

10. Adverse Events

Anticipated observations (e.g. common treatment effects) and adverse events occurring during the study will be recorded. Descriptions of anticipated observations and AEs will include the date of onset, the date it ended, the severity, the relationship to study device, and the outcome. All reported AEs

NOCTRIX H E A L T H

Clinical Trial

Investigational Plan, Protocol CT-05 (Extension Study)

Document #: CT-4

Rev: 1.0

Effective: 11/24/2021

will be summarized by the number of subjects reporting AEs, system organ class (where applicable), severity, seriousness, and relationship to study device.

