17.3.2. Safety Analysis

Frequency charts of adverse events occurring at any time during the study will be produced. The proportion of subjects in Arms 1 and 3 reporting one or more adverse events between study entry and Week 24 will be pooled and tabulated. Similar analyses will be done for SAEs and device-related SAEs. Safety analysis will include all subjects who were treated. A Statistical Analysis Plan (SAP) will be developed prior to completion of the first subject in Arm 1 or 3, which may include additional plans for safety analysis.

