8.3 Safety Analyses

The proportion of subjects having one or more adverse events (AEs) between study entry and Week 24 will be presented by Arm. The proportion of subjects reporting AEs between Week 25 and Week 32 will be presented for Arm 1. Similar analyses will be done for serious adverse events (SAEs), device-related SAEs, and device-related AEs

Adverse events will be coded using the Medical Dictionary for Regulatory Activities (MedDRA). AEs will be summarized at the subject level using counts and percentages by MedDRA system organ class (SOC) and preferred term (PT). AEs will also be summarized at the event level using

counts and percentages by SOC/PT and seriousness, by SOC/PT and severity, and by SOC/PT and relationship to the device.

Frequency charts of adverse events occurring at any time during the study will be produced. The proportion of subjects with at least one AE will be presented overall and by SOC. The proportion of subjects with at least one occurrence of individual AEs will be presented for AEs occurring in >3% of subjects overall or within either Arm.

This document, when printed, is valid only until its new revision gets released, or when it becomes obsolete in the eQMS. The user of a printed copy of this document is responsible for using the current revision and for discarding superseded or obsolete revisions. The most current version of this document always resides in the eQMS.

Noctrix Health, Inc. CONFIDENTIAL CL-7 v2.0

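### Timing is an axis of the safety endpoint in the synopsis but not in Section 17.3.1, and no summary described in the plan shows adverse event onset or duration within the 24 device-on weeks

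*Protocol*

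**What the plan says.** The safety endpoint row of the protocol synopsis reads "Descriptive analysis of adverse events, classified and tabulated by seriousness, relationship to the device, timing, and severity". Protocol Section 17.3.1 repeats the definition with three axes: "classified and tabulated by seriousness, relationship to the device, and severity".

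Protocol Section 17.3.2 sets out two outputs. One is the proportion of Arm 1 and Arm 3 subjects "reporting one or more adverse events between study entry and Week 24 will be pooled and tabulated". The other is a set of charts: "Frequency charts of adverse events occurring at any time during the study will be produced". The section also allows the SAP to add further safety analyses.

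SAP Section 8.3 works by Arm: "The proportion of subjects having one or more adverse events (AEs) between study entry and Week 24 will be presented by Arm". It adds a separate Weeks 25-32 proportion for Arm 1, and says that serious, device-related serious and device-related events will be handled similarly. Its event-level tables run "by SOC/PT and seriousness, by SOC/PT and severity, and by SOC/PT and relationship to the device". The titles of Tables 4.1 to 4.5 name no timing axis.

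Protocol Section 10 has the onset date, end date, severity, relationship and outcome recorded for each event. Section 9.1 describes the anticipated device observations as ones "which are typically mild to moderate, transient in nature, and resolve over time".

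**The concern.** The synopsis and Section 17.3.1 are both current text in the same protocol revision, and they define one endpoint differently. The SAP follows the shorter definition. SAP Section 3.5, which records departures from the protocol analyses, does not name this one; its closing sentence about other modifications is too general to show a decision.

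The stated objective is longer-duration efficacy, tolerability and adherence. SAP Section 9.0 gives efficacy a time course, with summaries at CT-05 Weeks 8, 16, 24 and 32. Safety has no counterpart inside the device-use period. A reader of the report would learn how many subjects had an event by Week 24. The planned summaries would not say whether new device-related events were still appearing late in that period, or how long events lasted. Any such statement would have to come from the listing after the data were seen, in an open-label study.

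**Working it through.** **1. Where timing appears**

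| Place | Axes or windows |
|---|---|
| Protocol synopsis | seriousness, relationship, timing, severity |
| Protocol 17.3.1 | seriousness, relationship, severity |
| Protocol 17.3.2 | entry to Week 24; charts over the whole study |
| SAP 8.3, subject level | entry to Week 24 by Arm; Weeks 25-32 in Arm 1 |
| SAP 8.3, event level; titles of Tables 4.1-4.5 | no timing axis |

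In Arm 1 the device is used in Weeks 1-24 and not in Weeks 25-32. The SAP's two windows therefore separate on-device from off-device time. Neither divides the 24 weeks of use.

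**2. What one proportion over 24 weeks leaves open**

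The documents give no adverse event rate and no sample size, so there is no plan figure to reproduce. As an illustration, let P be the proportion with a first event by Week 24, assumed between 10% and 40%.

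- Constant onset: weekly hazard h = −ln(1 − P)/24, and first onset by Week 4 = 1 − exp(−4h). For P = 30%, h = 0.3567/24 = 0.01486 and 1 − exp(−0.0594) = 5.8%.
- Front-loaded onset: 80% of first onsets by Week 4 (assumed), that is 0.8 × P.

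| P at Week 24 | By Week 4, constant | Share of first onsets | By Week 4, front-loaded |
|---|---|---|---|
| 10% | 1.7% | 17% | 8% |
| 20% | 3.7% | 18% | 16% |
| 30% | 5.8% | 19% | 24% |
| 40% | 8.2% | 20% | 32% |

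Within each row both patterns give the same entry-to-Week-24 figure. The Weeks 25-32 figure describes time after the device is returned, so it does not tell them apart either.

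**3. Where early exposure falls**

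Protocol Section 16.1 says subjects arrive with 4 weeks (sham then active) or 8 weeks (active throughout) of active use. Section 16.2 allows at most a 2-day gap before Arm 1. Adding 4 or 8 to the CT-05 week gives:

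| CT-05 weeks | Active exposure weeks, 4 prior | Active exposure weeks, 8 prior |
|---|---|---|
| 1-8 | 5-12 | 9-16 |
| 9-16 | 13-20 | 17-24 |
| 17-24 | 21-28 | 25-32 |

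No CT-05 period contains first exposure, and each period mixes two exposure ages. Onset counted from CT-05 Day 0 shows whether events continue to arise during extended use. To place them relative to first use, they must also be counted from the first active week in RESTFUL, or shown by RESTFUL assignment.

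**4. Onset and duration are different questions**

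Of the four groups of effects in Section 9.1, two are described as temporary while the device is worn and one is tied to active stimulation. That language is mainly about how long an episode lasts. A steady rate of short episodes would be consistent with it. End dates and resolution status bear on that statement; the onset tables in step 2 do not test it.

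**The case against.** The strongest reply is that the plan already classifies by time. The synopsis never defines timing, and an on-device versus off-device split is a timing classification that is also applied to serious and device-related events. This partly stands. A reader might infer that the SAP reports a single cumulative 24-week proportion, and SAP Section 8.3 does not support that, because it adds the Weeks 25-32 window. The single window describes only the proportion in protocol Section 17.3.2.

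A reader might also infer that the trial will be unable to tell early effects from continuing ones. The documents do not support that either. Onset and end dates are recorded, events are assessed at Evals 2 to 9 in Arm 1, and a by-subject listing is planned (SAP Listing 4). The distinction can be derived; it is simply not a pre-specified summary.

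It is tempting too to read Section 9.1 as a claim that onsets decline, or to project event rates beyond Week 24. Section 9.1 is a risk description about anticipated observations, qualified as typical, and mostly about episode length. No planned analysis extrapolates past the period of use.

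Two further points carry weight. The safety endpoint is descriptive and no sample size was set, so counts per period may be too small to say much. And the table shells in SAP Appendix A are not in the text available here; an onset column could exist in them. If so, Sections 17.3.1 and 8.3 should still say so.

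**Conclusion.** The point holds in a limited form. The protocol gives two versions of the safety endpoint that differ on timing. The SAP retains only the on-device versus off-device split, and no summary it describes shows onset or duration within the 24 device-on weeks.

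The consequence is modest. No efficacy result is affected, no data are lost, and the information can be recovered from recorded dates. What is missing is a pre-specified display of an axis that the synopsis itself names, in a study of longer-duration tolerability. The illustration shows that the missing detail could matter (at P = 30%, 5.8% against 24% of subjects with first onset by Week 4), but it rests on an assumed 24-week proportion and an assumed 80% front-loading. It is not an estimate for this device. The conclusion also rests on the SAP text and table titles alone. This is an inexpensive improvement rather than a fault that threatens the study's conclusions.

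**What to change.** - **Protocol Section 17.3.1:** restore timing, so that it agrees with the synopsis.
- **SAP Section 8.3 and the adverse event tables, Arm 1:** add subject-level counts of all and of device-related events by onset period, Weeks 1-8, 9-16 and 17-24. These end at Evals 4, 6 and 8. Use as denominator the subjects still on device at the start of each period.
- **Prior exposure:** present the same counts by time since first active exposure in RESTFUL, or by RESTFUL assignment (4 or 8 prior active weeks). SAP Section 9.0 already splits the efficacy measures by that assignment.
- **Duration:** for device-related events, report duration and the share unresolved at Week 24. State whether anticipated observations are counted here, since protocol Section 10 names them separately and Section 9.1 is about them.
- **SAP Section 3.5:** record the addition.

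The cost is a few table columns from dates already collected, plus the RESTFUL treatment assignment or first active date. The downside is small counts per period, so the tables should be read as description, without testing.
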